### *3.3.7 Withdrawal*

A subject who becomes inactive in the study due to, for example, physician recommendation, subject choice, loss to follow-up, or death, will be classified as “Withdrawal.”

After a subject has been withdrawn from the study or after a subject has withdrawn his/her consent, for any reason, Axonics will not actively collect any additional data after the point of withdrawal. All open adverse events should be closed or documented as chronic. Data collected up to the point of subject withdrawal may be used for analysis and all post-withdrawal adverse events will be recorded in the subject file.

For a subject that wishes to withdraw from the study, the investigator must deactivate the device, request return of all external components, and explant the device. Subject decisions must be fully documented on the final case report form. A statement personally signed and dated by the subject

about the decision to withdraw should be filed in the subject binder. The center will use the electronic database to document this decision process.

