### *5.2.2 Sample Size Justification*

The study sample size was initially determined considering that the primary endpoint analysis will be performed in the Trial Responders cohort. The sample size considerations using these assumptions is provided in detail in previous versions of the protocol (Rev A- Rev E).

Based on FDA input, the primary endpoint analysis cohort was changed to all implanted subjects. At this stage (rev F), all subjects have been enrolled and implanted. A justification for why the currently implanted number of subjects is a sufficient sample size is provided below:

The primary effectiveness endpoint hypothesis is that the proportion of all implanted subjects that are Treatment Responders at 6-months is greater than 50% (null proportion).

1. Previous literature on SNM for UUI treatment was used to estimate the expected success rate of all subjects receiving this treatment. These studies have shown approximately 80-85% of the subjects that receive an external trial proceed to a permanent SNM implant. Long-term (>6 month) clinical success is seen in approximately 80-85% of the subjects with permanent implant. Thus, of all subjects that received SNM therapy, approximately 65-70% are therapy responders at long term follow-up.
2. Assuming that the true proportion of Treatment Responders is 65%, one hundred and sixteen (116) implanted subjects at 6-months provides approximately 90% power to show that the percentage of Treatment Responders is greater than 50%, assuming a one-sided Type I error rate of 0.021. The one-sided Type I error rate of 0.021 is used to account for planned early look analyses (per the Statistical analysis plan).
3. Assuming an attrition rate of 20% between enrollment and the implant procedure due to screen failures and withdrawals, the total number of enrolled subjects will be capped at approximately one hundred and forty-five (145). Therefore, the study will continue to enroll subjects until either:
  - One-hundred and forty-five (145) patients are enrolled (“Enrollment Cap”), or

---

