### *5.2.4 Analysis methods*

#### *5.2.4.1 Primary Endpoint*

The primary effectiveness endpoint is that the proportion of all implanted subjects that are Treatment Responders is greater than 50% at 6-months post-activation. If the proportion of Treatment Responders is statistically greater than 50%, the study will be considered to be a success.

As mentioned above, a secondary endpoint analysis will also be conducted in subjects who are "Trial Responders" to allow for a direct comparison to the published SNM literature where analysis at follow-up visits are performed only in trial responders i.e. subjects that have  $\geq 50\%$  improvement in

symptoms after a one-month trial with an external stimulator.

The primary endpoint will be tested for significance based on a one-sided binomial test (such as Fisher's exact test) at a 2.1% significance level to account for two additional early looks as detailed in the Statistical Analysis Plan.

The primary safety endpoint of the study is the rate of adverse events (AEs) through 6-months.

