###### Missing not at Random (MNAR):

Subjects that are intraoperative screen failures or explanted or withdrawn due to adverse event(s) or lack of efficacy will be considered treatment failures and their baseline diary data will be used as the primary endpoint diary data.

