###### Missing at random (MAR):

Primary endpoint data for subjects who are missing at random (e.g., missed visits, incomplete data capture, withdrawals not related to safety or efficacy of device, death, loss to follow-up) will be imputed and analyzed using a multi-stage multiple imputation technique as follows:

- **Preliminary step:** the following variables will be considered in the multiple imputation procedure:
  - Age
  - Gender
  - Secondary diagnoses (stress incontinence, urinary frequency, retention, fecal incontinence, other, none)
  - Years since diagnosis of UUI

- Average daily number of urgency leaks at Baseline, Month 1, 2 and 3 visits.
- **Step 1:** Given the likely arbitrary missing data pattern, Markov Chain Monte Carlo (MCMC) method will first be used to impute just enough missing values among the variables to create a monotone missing pattern as needed for the monotone logistic regression imputation in Step 2.
- **Step 2:** A logistic regression model will be used to impute the missing values for the binary primary endpoint at Month 6 based on the partially imputed datasets created in Step 1. 200 imputed datasets will be created.
- **Step 3:** Each of the 200 imputed datasets created in Step 2 will be analyzed separately using binomial proportion estimation for the primary effectiveness endpoint at Month 6 to obtain parameter estimates of proportion and standard error.
- **Step 4:** Results obtained in Step 3 will be combined using the usual Rubin's rules for combining the imputed samples to account for variability of different imputations. This allows for a valid hypothesis test of the primary endpoint.

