### 8.6.1 Adverse Event Classification

**Adverse Event (AE)** – any untoward medical occurrence, unintended disease or injury, or untoward clinical signs (including abnormal laboratory findings) in subjects, users or other persons, whether or not related to the investigational medical device. This definition includes events related to any procedure in the protocol. The following are NOT considered AEs:

1. Any event expected to occur during the normal course of treatment that is not untoward.
2. Usual aches and pains following the surgical implant procedure. (Pain that is unusually intense or prolonged may be an AE.)
3. Unusual or uncomfortable sensations during the programming of the device or when the Remote Control is used to change stimulation settings. These occurrences are part of the usual standard of care. If the sensation is not resolved by reprogramming then the event may be considered an AE.
4. Change in the effectiveness of the SNM therapy may change over time, possibly requiring changes in programming parameters.
5. Underlying diseases, recorded at baseline, unless there is an increase in severity or frequency during the course of the investigation.
6. Death should not be recorded as an AE, but should only be reflected as an outcome of a specific SAE.

Any AE experienced by the study subject after informed consent, whether before, during or subsequent to the procedure, must be recorded in the eCRF.

**Adverse Device Effect (ADE)** – adverse event related to the use of an investigational medical device.

- a) This definition includes adverse events resulting from insufficient or inadequate instructions for use, deployment, implantation, installation, or operation, or any malfunction of the

investigational medical device.

- b) This definition includes any event resulting from use error or from intentional misuse of the investigational medical device.

**Serious Adverse Device Effect (SADE)** – An effect that has resulted in any of the consequences characteristic of a serious adverse event related directly to the investigational medical device.

**Serious Adverse Event (SAE)** – adverse event that:

1. Led to death
2. Led to serious deterioration in the health that either resulted in
  - a. a life-threatening illness or injury, or
  - b. a permanent impairment of a body structure or a body function, or
  - c. In-patient or prolonged hospitalization, or

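### Death before the 6-month diary is imputed as missing at random, while a death caused by an adverse event also fits the treatment-failure rule, and nothing says which applies

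*Combined protocol and SAP*

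**What the plan says.** The primary claim (section 5.2.4.1) is that "the proportion of all implanted subjects that are Treatment Responders is greater than 50% at 6-months post-activation". Section 5.2.4.6.1 divides missing 6-month outcomes into two classes.

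- **Missing not at random.** Subjects "explanted or withdrawn due to adverse event(s) or lack of efficacy will be considered treatment failures", and their baseline diary stands in for the 6-month diary. The adverse event need not be related to the device.
- **Missing at random.** The examples include "withdrawals not related to safety or efficacy of device, death, loss to follow-up". The binary 6-month response is imputed by logistic regression in 200 datasets and pooled by Rubin's rules.

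Two other sections bear on death. Section 3.3.7 gives the label of withdrawal to "A subject who becomes inactive in the study due to, for example, physician recommendation, subject choice, loss to follow-up, or death". Section 8.6.1 says: "Death should not be recorded as an AE, but should only be reflected as an outcome of a specific SAE".

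For secondary and exploratory diary endpoints, section 5.2.4.6.2 substitutes the baseline diary whenever the 6-month diary is missing.

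**The concern.** A subject who dies before month 6 as a result of an adverse event fits the failure class, because the subject became inactive through that event. The same subject also fits the imputed class, because death is named there. Two analysts could apply the text in good faith and reach different primary results.

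If the missing-at-random rule is followed as written, a subject with no possible 6-month diary can add to the responder count. In a single-arm test against a fixed 50% goal there is no control arm in which the same rule would offset this. Compared with counting the death as failure, imputation can only raise the estimate or leave it unchanged.

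**Working it through.** **1. The rules applied to one death before the 6-month diary**

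- Failure route: inactive because of death, so a withdrawal (3.3.7); the death is the outcome of a serious adverse event (8.6.1); withdrawal due to an adverse event is a failure (5.2.4.6.1, first class). Contribution to the responder count: 0.
- Imputation route: death is named in the second class. Contribution: the average imputed response q, between 0 and 1.
- Secondary endpoints: the baseline diary is used, so the same subject shows zero reduction in urgency leaks (5.2.4.6.2).

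**2. What the imputation model knows.** Its listed variables are age, gender, secondary diagnoses, years since diagnosis, and daily urgency leaks at baseline and Months 1, 2 and 3. None describes the fatal event. The value of q is therefore driven largely by the subject's early leak counts.

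**3. The plan's own figure.** Section 5.2.2 states that "one hundred and sixteen (116) implanted subjects at 6-months provides approximately 90% power", with a true rate of 65%, a null rate of 50% and one-sided alpha 0.021. By the normal approximation with null variance in the critical value:

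Power = Φ[(0.15 × √116 − 2.0335 × 0.5) / √(0.65 × 0.35)] = Φ[(1.6155 − 1.0168) / 0.4770] = Φ(1.255) = 89.5%.

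The stated figure reproduces. It does not depend on the death rule.

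**4. Size of the effect.** The documents give no death count or rate, so k = 0 to 3 deaths is an assumption, as is q = 0.65 (the planning rate). The rise over counting deaths as failures is k × q / 116. With survivors responding at 65%, the rate with deaths as failures is (116 − k) × 0.65 / 116.

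| Deaths k | Rate, deaths imputed | Rate, deaths as failures | Difference (points) |
|---|---|---|---|
| 0 | 65.0% | 65.0% | 0 |
| 1 | 65.0% | 64.4% | 0.56 |
| 2 | 65.0% | 63.9% | 1.12 |
| 3 | 65.0% | 63.3% | 1.68 |

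If q were 0.80, the difference would be 0.80 / 116 = 0.69 points per death. The ceiling, at q = 1, is 1 / 116 = 0.86 points per death.

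**5. Variance.** At 65% the within-imputation variance is 0.2275 / 116 = 0.001961, a standard error of 4.43 points. With the model coefficients held fixed, three imputed deaths add a between-imputation variance of 3 × 0.2275 / 116² = 0.0000507. With Rubin's factor (1 + 1/200) this is 0.0000510. The total is 0.002012, a standard error of 4.49 points. The pooled test thus gives back a little of the gain, but the shift of 1.68 points is much larger than the 0.06-point rise in the standard error.

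**The case against.** The strongest defence is that the plan names death explicitly in one place and nowhere in the other, so the specific rule governs. The conflict appears only when sections written for other purposes are joined. Section 3.3.7 is a disposition label, and it also calls loss to follow-up a withdrawal, which nobody would treat as failure on that ground. Section 8.6.1 is a coding instruction for the adverse event form. This much stands: a reader might infer that the plan's definitions make every death a treatment failure, and the documents do not go that far. What remains is an overlap for deaths caused by an adverse event, with no order of priority.

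A reader might also infer that even a device-related death would be imputed as a probable responder. That is not established. The list is introduced as examples, and imputation is said to follow the circumstance of the missing data, so an analyst could send such a death to the failure class. The imputed value also depends on the Month 1 to 3 leak counts, so a subject doing poorly would tend to be imputed as a non-responder.

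A third tempting reading is that one imputed death could tip the trial between 69 and 70 responders. Exact binomial tails under 50% are indeed 0.0254 for 69 or more of 116 and 0.0161 for 70 or more. But that is not the boundary of the pooled test. At 69/116 = 0.5948, an estimate-over-standard-error test gives z = 0.0948 / 0.0456 = 2.08 (p about 0.019) with the estimated variance, or 0.0948 / 0.0464 = 2.04 (p about 0.0205) with the null variance. Both are below 0.021. A death also adds a fraction of a responder and not a whole one.

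Finally, section 5.2.4.7 already covers the case in which every missing value is a non-responder. No further tipping-point request is needed. It is a sensitivity analysis, however, and section 5.2.4.1 declares success on the primary test.

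**Conclusion.** The point holds as an unresolved overlap in the primary missing-data rule, with a bias towards success if the missing-at-random rule is followed. Under an assumed 0 to 3 deaths before the 6-month diary, imputed at about 65%, the pooled responder rate rises by 0 to about 1.7 points on 116, slightly offset by the added between-imputation variance. With no such deaths the effect is nil, and deaths after the 6-month diary do not matter.

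It is still worth correcting. The rule belongs to the primary analysis, imputation assumes an outcome that a deceased subject cannot have, and the same death is handled in the opposite direction for the secondary diary endpoints. Section 5.2.3.1 refers to a Section 11.4 for imputation details. This conclusion rests on the text of 5.2.4.6.1.

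**What to change.** Remove death from the missing-at-random examples in section 5.2.4.6.1, and make the same edit in the SAP. State that death before the 6-month diary counts as Treatment Non-responder in the primary analysis. At minimum, apply this to any death resulting from an adverse event, which agrees with the existing failure rule. Section 3.3.6 reserves the term Non-responder for subjects with analyzable data, so use the device already in the failure rule and let the baseline diary stand as the 6-month diary. Report imputation of deaths as missing at random as a sensitivity analysis.

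The edit is one line in each document and affects no clinical procedure. Its cost is a slightly lower responder rate if deaths occur. If survivors respond at 65%, nothing else is missing and the exact test is used (70 of 116 needed), power is 87.4% with no deaths and 84.8%, 81.7% and 78.3% with one, two and three deaths. The change should be made without reference to any deaths observed, since section 7.2 says sponsor personnel are not blinded to results.

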#### *5.2.4.6.2 Secondary and Exploratory endpoints*

For secondary and exploratory endpoint analyses that use subject-reported outcomes/ questionnaires, missing data will be addressed by the specific scoring guideline provided by the questionnaires. In the cases where the response does not contribute to a score, no imputation will be performed. Subjects with missing or incomplete diaries at 6 months will be included in the secondary/exploratory endpoint analysis by using their Baseline diary data.

#### *5.2.4.7 Tipping point analysis*

A sensitivity analysis of tipping point will be performed to assess the robustness of the primary endpoint results. Tipping point analysis will summarize all possible combinations of missing data, where each missing value is replaced with either Treatment Responder or Non-responder.

## 6 RISK/BENEFIT ANALYSIS

### 6.1 Risks

A risk assessment in accordance with ISO14971:2012 was conducted.

The risks of complications associated with implanting the Axonics SNM System are comparable with general risks associated with any standard surgical procedure. The following risks and discomforts have been identified in relation to the SNM therapy:

- Worsening of bladder and/or bowel function
- Allergic or immune system response to the implanted materials
- Change in sensation or magnitude of stimulation which has been described as uncomfortable by some subjects
- Infection
- Pain or irritation at Neurostimulator and/or Tined Lead site
- Seroma, hemorrhage, and/or hematoma
- Tined Lead or Neurostimulator migration or erosion
- Nerve injury (including numbness)
- Technical device malfunction
- Transient electric shock or tingling
- Unintended nerve activation
- Heating or burn at Neurostimulator site

The risks of the procedure include exposure to anesthesia and exposure to radiation from fluoroscopy. These risks are the same as expected from the procedure of the commercially available SNM system.

The risks associated with participation in this study will be similar to those associated with commercially available SNM therapies. The risks of participation in this study will be minimized by careful subject and site selection, as well as by implementing monitoring procedures to ensure proper conduct and management of the study.

Consult the device manuals for additional information regarding the risks associated with the Axonics SNM System. Any safety directive from Axonics to the ARTISAN-SNM investigators will be reported according to applicable regulations.

In case of any unexpected Adverse Device Effect or Serious Adverse Device Effect, investigators will be informed. Investigators shall forward this information to their IRBs/ECs as per local requirements. Any unexpected Adverse Device Effect or Serious Adverse Device Effect will be reported by Axonics in accordance with applicable US FDA regulations.

## 6.2 Risk-Benefit Analysis

As noted in Section 1.2, the commercially available InterStim device has been shown to have a favorable risk-benefit profile, especially given the low incidence of adverse events and significant improvements in quality of life with SNM therapy.

The Axonics SNM System has been thoroughly tested to ensure that the device will perform as anticipated, and the benefits of the system are expected to be similar to the InterStim device.

Results from the RELAX-OAB post-market follow-up study indicate that the Axonics SNM System has a similar safety and effectiveness profile to the InterStim device.

The use of the device is designed to protect the health and safety of the patient, user, and environment. Therefore, the device is appropriate for the intended use, the potential benefits of the device outweigh the risks, and all the applicable risks have been addressed through appropriate testing and any residual risks are acceptable when weighed against the potential benefits to the patient.

## 7 INVESTIGATOR AND SPONSOR RESPONSIBILITIES

### 7.1 Investigator Responsibilities

This study will be conducted in accordance with ISO 14155: 2011 guidelines, which provides a detailed description of the investigators' responsibilities. The investigator is responsible for conducting the study in accordance with the Protocol, the signed Investigator Agreement and other agreements, applicable laws and regulations, and any conditions of approval imposed by the reviewing IRBs/ECs and/or FDA/Competent Authority (where applicable). To ensure compliance with the guidelines, the sponsor, an independent body, or a regulatory agency may audit the study. By agreeing to this Protocol, the investigators and their institutions accept to allow monitoring, audits, IRBs/ECs review, and regulatory inspections that are related to the study. They also agree to provide authorized individuals with access to source data and documentation as well as the right to copy records, provided such activities do not violate subject consent and subject data confidentiality.

If the subject or investigator refuses to follow the Clinical Trial Protocol, the study device(s) should be deactivated or explanted, and the subject(s) withdrawn from the study. Axonics will formally communicate with the Investigator in an attempt to maintain compliance. This communication should consist of at least three documented communication attempts including a certified mail. Continued non-compliance by a subject may result in withdrawal from the trial. Continued non-compliance by the investigator may result in removal of the investigator from the trial. Escalation to the IRB/EC and/or Competent Authority may also be necessary.

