### *3.3.8 Subject Lost to Follow-up*

If a subject is lost to follow-up, the investigator should make a good faith effort to contact the subject with at least three (3) documented communication attempts (at least one of which must be in writing). The investigator should inform the subject of the option to withdraw.

If a subject relocates during the clinical trial, efforts will be made to maintain the subject in the study if reasonable travel expenses allow continued participation, provided payment of travel expenses by the sponsor is permitted by applicable law. Alternatively, the subject may be transferred to another clinical trial site, if one is available in the new geography. If the subject cannot be transferred to another clinical site, then the investigator will withdraw the subject from the study as described above.

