## **3.4 Subject Care**

The following sections contain general guidance on dealing with device explant and/or replacement. Axonics does not recommend the removal of the implanted Neurostimulator except in cases of uncontrolled infection, suspected damage to surrounding tissues that may be worsening because of the implant, or intolerable side effects that are not mitigated with inactivating the system.

The decision to explant or replace an implanted device should be made by the subject with appropriate counsel by the physician on procedural risks. A qualified physician who has been trained in the implant/explant of the Axonics SNM System must perform these procedures according to the device manuals.

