### *3.4.3 Deactivating the Axonics SNM System*

In some cases, the subject may elect to leave the device implanted, but no longer activated. Leaving the Tined Lead and/or Neurostimulator implanted does not add significant risk to the subject.

Subjects who elect to leave a device implanted that is not activated must return their external devices to the clinical site.

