#### 3.5.3 Clinical Site Closure

Axonics, with or without advice from the DSMB, reserves the right to close a clinical site at any stage based on reasonable written notice to the investigator.

The investigator may also discontinue participation in the study with reasonable written notice to Axonics.

Should either of these events occur, the investigator shall:

- return all documents and devices to the sponsor
- provide a written statement as to why the investigator would like to discontinue participation
- notify the Ethics Committee and the regulatory authority (as applicable)
- arrange for continued follow up of already enrolled participants (as applicable)

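### Section 7.1, read literally, ends therapy and follow-up for compliant subjects when only the investigator refuses the protocol; this conflicts with the rest of 7.1 and, more narrowly, with 3.5.3

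*Combined protocol and SAP*

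**What the plan says.** Section 7.1 (Investigator Responsibilities) opens its paragraph on non-compliance with one rule for two triggers: "If the subject or investigator refuses to follow the Clinical Trial Protocol, the study device(s) should be deactivated or explanted, and the subject(s) withdrawn". The sentence has no exception for a subject who is following the protocol, and it refers to no other section.

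The sentences after it treat the two parties separately. The sponsor makes at least three documented attempts to bring the investigator back into compliance. A subject's own persistent non-compliance may lead to that subject's withdrawal. For the other party, "Continued non-compliance by the investigator may result in removal of the investigator from the trial". Escalation to the ethics committee or authority is also possible.

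Other sections bear on the same situation:

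- Section 3.5.3: when the sponsor closes a site or the investigator discontinues, the investigator is to "arrange for continued follow up of already enrolled participants (as applicable").
- Section 3.3.8, for subjects who relocate: transfer to another site is considered first, and "If the subject cannot be transferred to another clinical site, then the investigator will withdraw the subject from the study as described above".
- Section 3.4: "The decision to explant or replace an implanted device should be made by the subject with appropriate counsel by the physician on procedural risks". The sponsor also advises against removing the neurostimulator outside a short list of medical reasons.
- Section 3.4.3: "In some cases, the subject may elect to leave the device implanted, but no longer activated".
- Section 3.3.7: after withdrawal "Axonics will not actively collect any additional data after the point of withdrawal", although "all post-withdrawal adverse events will be recorded in the subject file". For a subject who wishes to withdraw, the same section requires both deactivation and explant.
- Section 8.16 requires strict adherence to every protocol item unless a subject's well-being calls for something else.

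**The concern.** Tying deactivation and withdrawal to a subject's own refusal is understandable. Tying them to the investigator's refusal places the cost on people who have done nothing wrong. A subject who is benefiting could have stimulation switched off and study visits ended for a reason that is neither medical nor their own choice.

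What is at stake is subject protection and the remaining long-term follow-up. Because Section 8.16 asks for strict adherence, a site or monitor could act on the sentence as it stands.

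**Working it through.** No alpha, power or effect size enters this point, and the plan gives no figure to reproduce. The check sets the provisions side by side and then bounds the follow-up at stake.

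**Within Section 7.1**

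1. First sentence: the trigger is refusal by either party, and the consequence falls on devices and subjects.
2. Later sentences: the trigger is continued non-compliance by a named party, and the consequence falls on that party. For the investigator it is removal, which *may* follow. No consequence for subjects is named.
3. For an investigator who refuses, the first sentence therefore withdraws subjects, while the later ones try to restore the investigator's compliance and then possibly remove that investigator. Nothing says which governs. This conflict is direct.

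**Section 7.1 against Section 3.5.3**

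4. Section 3.5.3 applies on site closure or investigator discontinuation, not on refusal as such, and its follow-up duty is qualified by *as applicable*.
5. The two sections meet only when a refusing investigator stops, or when the sponsor closes that site. In that case one asks for withdrawal, which ends active data collection under 3.3.7 apart from adverse-event recording. The other asks for follow-up to continue. If that means study visits, a subject cannot have both.
6. Section 3.5.3 gives the duty to the investigator, who here is the refusing party. It is therefore a weak safeguard in this situation.

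**Upper bound on remaining follow-up under Rev G**

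Inputs: Rev F is dated 06-Nov-2018 and Rev G 11-Feb-2019 (Revision History). All subjects were implanted by Rev F (5.2.2). Activation is 0 to 14 days after implant (4.1.3). The last visit is nominally Day 730 (Table 1). It is assumed that the 14-day limit was kept.

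- Rev F to Rev G: 24 (November) + 31 + 31 + 11 = 97 days.
- Minimum time since activation for any subject at Rev G: 97 − 14 = 83 days.
- Maximum time remaining to Day 730: 730 − 83 = 647 days, about 21 months.

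Rev F gives only the latest possible date of the last implant, so 83 days is a minimum and 647 a maximum. No minimum number of remaining visits follows. For example, if the last implant was 117 days before Rev F, every subject was at Day 97 + 117 − 14 = 200 or later at Rev G. The 6-month window (Day 180 ± 20) would then already have been reaching its end or be past.

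The 647 days bound lost follow-up, not lost therapy. Section 3.5.1 lets subjects who complete the final visit go on using the device.

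**Number of subjects**

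The documents do not give subjects per site. As an illustration only, the planned 116 implants over the maximum of 20 sites average 116 / 20 = 5.8.

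**The case against.** The strongest reply is that the paragraph largely explains itself. The verb is *should*, party-specific steps follow at once, and the likely intent is a separate remedy for each party. The bracketed plurals in the sentence could mean only the subjects affected by a refusal, and no timing is given. Section 8.16 also lets a site depart from the text to protect a subject's well-being. Finally, the device had no US marketing approval, so there is some reason to stop stimulation when nobody is following the protocol.

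Much of this stands, and it keeps the point small. It does not remove it. The intended reading has to be supplied by the reader, and the sentence still names the investigator's refusal as sufficient.

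A reader might also infer stronger things that the documents do not support:

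- *That compliant subjects must undergo explant surgery.* Section 7.1 offers deactivation as an alternative, so Section 3.4 need not be breached.
- *That deactivation is always the subject's choice.* Section 3.4.3 describes elective deactivation, but 3.4.1 calls for it when a subject declines lead replacement, 3.5.1 mentions mandated deactivation, and 3.5.2 allows it for a safety concern.
- *That 3.5.3 is contradicted whenever an investigator refuses.* It is engaged only on closure or discontinuation. Section 3.3.8 is an analogy, since it concerns relocation.

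**Conclusion.** The point holds as a defect of wording. Section 7.1 as written makes the investigator's refusal enough to end therapy and active data collection for a compliant subject. That conflicts directly with the remainder of 7.1 and, in the narrower circumstances above, with 3.5.3.

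The effect on the primary result is negligible. The trigger is rare, and under 5.2.4.6.1 withdrawals unrelated to safety or efficacy are multiply imputed. The loss per affected subject is at most 647 days of scheduled follow-up under Rev G, given the activation assumption, plus loss of active therapy for a period the documents do not bound. It would be wrong to infer that some fixed set of visits is certainly still ahead, or that the sponsor intends the literal result; the later text of 7.1 suggests otherwise.

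The change is worth considering because it protects subjects at almost no cost.

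**What to change.** In the Section 7.1 sentence, delete the words that make the investigator's refusal a trigger. Then add:

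1. When an investigator refuses the protocol or is removed, the sponsor, not the departing investigator, arranges continued therapy and scheduled follow-up under a replacement investigator or at another site.
2. Such subjects are withdrawn only if neither arrangement is possible or the subject chooses to withdraw.
3. For these withdrawals explant is not automatic. It follows Section 3.4 (the subject's decision with physician counsel), as a stated exception to the explant requirement in Section 3.3.7. Without this exception, a subject who chose to withdraw would meet the mandatory explant there.

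Add cross-references to 3.3.7, 3.4 and 3.5.3.

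The cost is wording in the next protocol revision, with no new data, visits or analyses. In use there would be minor transfer logistics, since a receiving site may not be nearby, and approval of the replacement investigator. Section 7.1.2 covers sponsor approval of co-investigators but describes no route for replacing a principal investigator, so the new text should name one.
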